#### **4.7.5 Concomitant Medications**

Concomitant medications include any medication being used at any time from first dose of study drug through to day of study discontinuation/completion, or medication being used at any time up to the start of study treatment. The data will be summarized, and report the total number of patients taking at least one medication, and total number of medications. Summaries will also be split by medication class and preferred medication.

All summaries and listings of concomitant medications will be based on safety population and specified in the LoPO.

#### **4.8 MISSING DATA**

The handling of intercurrent events explained in the individual studies will be applied before using the missing data handling approaches in this section. The handling of intercurrent events will occur in the order the intercurrent event occurs within the study.

To assess the robustness of the primary endpoint, a tipping point analysis will be conducted. The tipping point is defined as the difference in the number of missing events (i.e., remission) between the treatment groups that result in a change in the primary outcome conclusions (Yan et al. 2009). A two-dimensional plot will be produced for each primary comparison of etrolizumab (105 mg) vs. the comparator to evaluate where the tipping point lies.

The tipping point analysis will be used to assess the robustness of the primary endpoints within each study. The following groups of patients will always be considered nonremitters/non-responders within the tipping point analysis.

- Patients whose remitter/responder status can be calculated as a non-remitter/non-responder from their available sub scores, even when not all four MCS subscores are available.
- Patients who have received rescue therapy during the study.
- Patients who have discontinued study treatment early.

For all continuous endpoints, a MMRM model will be fitted to analyse UC-PRO domains assuming the data is missing at random. For missing SF/RB and IBDQ data single imputation worse observation carried forward (WOCF) post baseline will be applied to missing data, including when data is missing due to intercurrent event. An additional sensitivity analysis using observed case will be conducted, to assess the robustness of the analysis. All summary data will be reported using no imputation for missing data.

For any missing baseline data, no imputation of results data will be applied, and therefore, any endpoints requiring comparison back to baseline results will also be set to missing. To prevent a missing SF/RB subscore at baseline or post baseline which would lead to a missing MCS/mMCS/pMCS score, the anchor date used for selecting diary data to calculate RB/SF subscores can be imputed. If bowel prep date is missing, then endoscopy date can be used; if the endoscopy date is missing then the visit date can be used as the anchor date. If the PGA visit date is missing, the visit date will be imputed as Day 1+x weeks to allow RB and SF scores to be calculated.

No imputation will be applied for missing laboratory or vital signs data.

An AE with a completely missing, non-imputed start date will be assumed to be treatment-emergent, unless the AE has a complete, non-imputed end date that is prior to the date of the first dose.

All deaths will be reported, regardless of completeness of death date.

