6.4 EFFICACY ANALYSES

Analyses of the efficacy endpoints will include all patients randomized into the Maintenance Phase (i.e., patients who achieved a clinical response at Week 10 in the open-label Induction Phase) with patients grouped according to the treatment assigned at randomization (intent-to-treat population).

To manage the overall type I error, the primary and secondary endpoints in the Maintenance Phase will be tested sequentially. Each endpoint will be tested at a two-sided 5% significance level. The testing hierarchy for the secondary endpoints will be described in the SAP.

Patients who are non-evaluable for efficacy at a specific timepoint (e.g., because of missing data or transfer to the OLE treatment protocol) will be considered non-responders for all response/remission type endpoints. In addition, for the Maintenance Phase, patients who initiated an agent not allowed in combination with etrolizumab (see Section 4.4.2), an immunosuppressant or corticosteroid (administered for the treatment of UC), or who had an increase in dose over baseline levels for treatment of worsening disease symptoms will be considered non-responders thereafter. In the Induction Phase, initiation of an agent not allowed in combination with etrolizumab, an immunosuppressant, oral or topical 5-ASA, or corticosteroid, or an increase in dose over baseline levels will lead to non-responder classification.

For continuous outcomes (e.g., IBDQ, UC-PRO/SS), scores after the first use of rescue medication will be imputed using the worst post-baseline score from the following assessments: the last score available prior to the start date of first rescue medication and all scores available after the start date of rescue medication use.

In addition to the analyses described herein and in Section 6.4.1 and Section 6.4.2, the following analyses will be performed for the primary efficacy endpoint and key secondary efficacy endpoints. Details of these analyses will be described in the SAP:

- Sensitivity analyses to evaluate the robustness of results to the primary analysis methods (e.g., handling of dropouts)
- Subgroup analyses to evaluate the consistency of results across prespecified subgroups (e.g., based on age, sex, race/ethnicity, baseline UC medications, baseline corticosteroid dose)

Further details, including additional missing data handling rules, *and further definitions of exploratory endpoints* will be provided in the SAP.

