Appendix 1 Schedule of Activities (cont.)

- ^r A blood sample to test for antibodies to JCV will be taken and stored for possible later assessment of how widespread the JCV infection is in the study population. Sample testing for the presence of JCV antibodies is not helpful in predicting risk for PML or for evaluating neurologic symptoms. The sample may be tested if there is a strong belief that this information will be helpful in managing a patient's condition.
- ^s Endoscopy + rectal bleeding assessment + stool frequency assessment + Physician's Global Assessment. Patients who have not undergone full colonoscopy with documented results within 1 year prior to screening should undergo colonoscopy in lieu of sigmoidoscopy at the screening visit to allow for screening for cancer/dysplasia (yes/no).
- ^t During screening, patients must be trained on the use of the e-diary. Patients are to complete the e-diary on a daily basis for the stool frequency and rectal bleeding score (for MCS/pMCS), starting from the first screening visit, and for at least 9–12 consecutive days around the time of each scheduled visit for the UC-PRO/SS.
- ^u Screening endoscopy (for the MCS) should be performed 4–16 days prior to Day 1 (i.e., Day –16 to Day –4). For baseline measurements, the Physician's Global Assessment will be obtained only once, on Day 1 (prior to enrollment), and the Physician's Global Assessment score will be used to calculate both the baseline (screening) MCS and the baseline (Day 1) pMCS.
- ^v Rectal bleeding assessment + stool frequency assessment + Physician's Global Assessment.
- ^w For culture and sensitivity testing; ova, parasites, and Clostridium difficile toxin testing.
- ^x Sample analyses may include, but are not limited to, analyses of fecal calprotectin and other exploratory PD biomarkers (such as analyses of the microbiota and bacterial cultures).
- ^y IF REQUIRED: Only if there is suspicion for clinically significant CMV colitis, one biopsy sample should be obtained from the base of the ulcer to evaluate for histological presence of CMV. Analysis should be performed locally if possible, or can be sent to a central laboratory if necessary. Result must be negative for CMV prior to dosing on Day 1.
- ^z IF REQUIRED: If patient does not have previously documented histopathologic confirmation of UC as defined in the inclusion criteria, one biopsy sample can be obtained from the base of the ulcer read locally for histopathologic confirmation of UC.

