#### **4.4.2.3.1 Functional and Bowel Domain**

Two domain scores computed for the UC-PRO Signs and Symptoms:

- Functional Symptoms
- Bowel Movement Signs and Symptoms

There is no single total score. The questions contributing to each domain are shown in [Appendix 6](#). The functional domain score ranges from 0–12, the bowel domain score ranges from 0–27, with a higher score indicating a worse disease state. The responder definition cutoffs for the Functional and Bowel domains will be pre-specified in the Data Analysis Plan (DAP).

The daily scores contributing to the UC-PRO/SS calculation for a visit will be selected as: most recent 7 daily scores available prior to but not including a visit. (Note: a minimum of 4 days is required.)

For each item in the questionnaire, a score will be calculated for a visit by taking the average of the most recent 7 daily scores available. The domain score for a visit will then be determined, taken as the sum of the (averaged) items for each question.

The endpoint using the UC-PRO/SS is the change from baseline at Week X in UC-PRO/SS Domain as assessed by UC-PRO/SS measure.

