#### **Change from Baseline at Week X**

$$= \text{Week X UC-PRO/SS Domain Score} - \text{Baseline UC-PRO/SS Domain Score}$$

A MMRM (Mixed Model Repeated Measures) analysis will be performed to assess the change from baseline in UC-PRO domains at Week X and will include the fixed categorical effects of treatment, visit, study stratification factors, and treatment-by-visit interaction, and the continuous covariates of the baseline continuous UC-PRO domain and baseline UC-PRO domain-by-visit interaction. An unstructured covariance matrix will be used to model the within patient errors within the MMRM.

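### Patients without a usable Week 0 score drop out of the UC-PRO/SS and IBDQ comparisons although their post-randomisation data could be kept; the cost is modest precision, not bias

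*SAP*

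**What the plan says.** Project SAP 4.8 leaves missing baseline data unimputed and states that "any endpoints requiring comparison back to baseline results will also be set to missing". For IBDQ, "single imputation worse observation carried forward (WOCF) post baseline will be applied to missing data", which fills gaps after baseline only.

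Project SAP 4.4.2.3.1 defines the outcome: "The endpoint using the UC-PRO/SS is the change from baseline at Week X in UC-PRO/SS Domain". Its MMRM also carries "the continuous covariates of the baseline continuous UC-PRO domain and baseline UC-PRO domain-by-visit interaction". A visit's UC-PRO/SS score uses the "most recent 7 daily scores available prior to but not including a visit. (Note: a minimum of 4 days is required". Project SAP 4.4.2.4 analyses change in total IBDQ by ANCOVA, with baseline IBDQ as a covariate.

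Baseline is the last assessment before the first induction dose (study SAP 2.2). Randomisation follows within two weeks of the Week 10 timepoint (Protocol Appendix 1, footnote ee). Study SAP 4.1.2.1 applies the mITT set (randomised and dosed in maintenance) to maintenance efficacy analyses and names one exception, histologic remission.

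**The concern.** Read together, these sections remove a randomised, treated patient from two comparisons because of a gap that arose before randomisation. The schedule has 14 UC-PRO/SS assessments from Week 12 to Week 62; for such a patient all 14 change scores are missing and none is used. The MMRM's missing-at-random assumption cannot help, because it needs at least one observed outcome per patient. Carrying forward the worst post-baseline IBDQ score cannot help either, because the baseline to be subtracted is absent.

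This acts as a second exception to mITT that study SAP 4.1.2.1 does not state. It matters most for UC-PRO/SS: project SAP 4.4.2.3 calls its two signs-and-symptoms domains key endpoints, and the study SAP does not place them outside the multiple testing procedure, as it does IBDQ (4.4.2.12). Stool frequency and rectal bleeding have fallback rules in project SAP 4.8 and Table 2 to avoid a missing subscore. UC-PRO/SS and IBDQ have none at baseline.

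**Working it through.** **1. The plan's own figure.** The documents give power only for the remission endpoint: 105 per arm, 25-point difference, placebo rate 30–45%, two-sided 5% chi-squared test, power above 90%. Recomputed power is 96.1% at placebo rates of 30% and 45%, and 95.75% at 35% and 40%. The figure reproduces and this point does not affect it. No standard deviation, effect size or power is given for UC-PRO/SS or IBDQ, so the values of m, ρ and effect size below are assumptions.

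**2. Is the subtraction needed?** With outcome Y, baseline B and treatment T, suppose Y − B = a + δT + βB. Then Y = a + δT + (β + 1)B. The treatment coefficient δ is unchanged; only the slope on B moves by 1. With a baseline-by-visit term the same shift occurs at every visit. In simulated ANCOVAs the two estimates of δ differed by at most about 1e-15. For the treatment contrast, Week 0 therefore works as a covariate, although the endpoint as written also subtracts it.

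**3. Is there bias?** Missingness at Week 0 precedes randomisation, so it is independent of arm. In 6,000 simulated trials per setting (105 per arm, true effect −0.45 SD, missingness depending on baseline), mean estimates lay between −0.447 and −0.451 when patients were dropped and between −0.448 and −0.452 when they were kept by mean fill plus indicator. Neither analysis is biased.

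**4. Precision.** Let m be the share of the 210 randomised patients without a usable baseline and ρ the baseline/outcome correlation, treated as a single-visit ANCOVA.

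- Standard error when dropping is proportional to √[(1 − ρ²)/(1 − m)].
- Standard error when keeping everyone with a mean-filled covariate is proportional to √[(1 − m)(1 − ρ²) + m].

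Example, m = 0.05 and ρ = 0.5: √(0.75/0.95) ÷ √(0.95 × 0.75 + 0.05) = 0.8885 ÷ 0.8732 = 1.0175.

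| Assumed m | Patients of 210 | Excess SE, ρ = 0.3 | ρ = 0.5 | ρ = 0.7 |
|---|---|---|---|---|
| 1% | 2 | 0.5% | 0.3% | 0.0% |
| 2% | 4 | 0.9% | 0.7% | 0.1% |
| 5% | 10–11 | 2.3% | 1.8% | 0.2% |
| 10% | 21 | 4.9% | 3.7% | 0.7% |

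The simulations in step 3 gave 2.5% and 5.6% at ρ = 0.3, and 1.9% and 4.3% at ρ = 0.5, for nominal m of 5% and 10%. Realised missingness there was slightly above nominal, about 5.5% and 10.9%.

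The two standard errors are equal when 1 − ρ² = (1 − m)/(2 − m), that is at ρ of about 0.71 to 0.73 for m of 1–10%. Above that, a plain mean fill is slightly worse than dropping.

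**5. Power, for scale.** Compared with having every baseline, dropping inflates the standard error by 1/√(1 − m): 0.5%, 1.0%, 2.6% and 5.4% at m = 1%, 2%, 5% and 10%. At an assumed standardised effect of 0.45, power falls from 90.3% to 90.0%, 89.8%, 88.8% and 87.1%. Mean filling recovers only part of this.

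**6. How likely is a missing Week 0 UC-PRO/SS score?** Project SAP 4.4.2.3 places the 9–12 diary days before the visit. With 9 such days and an assumed 85% daily completion, independent across days, P(fewer than 4 entries) = P(Bin(9, 0.85) ≤ 3) = 0.06%; at 70% completion it is 2.5%.

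**The case against.** The strongest reply is that nothing is invalid: both analyses are unbiased, no document shows that any randomised patient is affected, and at 1–2% missing the gain is below 1%. All of that stands. IBDQ is also a single questionnaire completed at the site on Week 0 and lies outside the multiple testing procedure, so that limb carries less weight.

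Three stronger readings are tempting, and the documents do not support them.

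- **That a protocol rule is broken.** Protocol 6.4 says "Analyses of the efficacy endpoints will include all patients randomized into the Maintenance Phase", but the same section leaves additional missing-data rules to the SAP, and Protocol 6.4.2 itself specifies an ANCOVA that needs the baseline value. What can be said is that the analysed set falls short of the SAP's own mITT set and no method is given to retain these patients.
- **That a large share may lack a Week 0 score.** Protocol Appendix 1 asks for diary entries "for at least 9–12 consecutive days around the time of each scheduled visit for the UC-PRO/SS". If only 4, 5 or 6 of those days preceded Day 1, the chance of fewer than 4 entries at 85% completion would be 48%, 16% or 5%. Project SAP 4.4.2.3, which governs this endpoint, puts the days before the visit, and the chance is then near zero.
- **That clinical response is affected.** Under Protocol 6.4 non-evaluable patients "will be considered non-responders for all response/remission type endpoints", which sits awkwardly with setting an endpoint to missing. But randomisation already required a Week 10 response measured against baseline MCS, so, barring a deviation, no randomised patient lacks it.

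**Conclusion.** The point holds as one of efficiency and of agreement with the stated analysis set. An mITT patient without a usable Week 0 score contributes nothing to the UC-PRO/SS MMRM or the IBDQ ANCOVA, whatever was recorded after randomisation, and study SAP 4.1.2.1 does not say so. There is no bias between arms. At an assumed 1–10% missing, the standard error is roughly 0–5% above that of an analysis keeping everyone.

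This rests on an assumed missing share, an assumed correlation of 0.3 to 0.7 and a single-visit approximation to the MMRM. If the diary days precede the visit as project SAP 4.4.2.3 states, the UC-PRO/SS loss through short diaries is probably at the bottom of that range. The change is worth making because it costs almost nothing, not because a conclusion is likely to turn on it.

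**What to change.** In project SAP 4.8 and 4.4.2.3–4.4.2.4:

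- fit the MMRM and ANCOVA to the visit score, with baseline (and baseline-by-visit in the MMRM) as covariate;
- fill a missing Week 0 covariate with the pooled mean over both arms, computed blind to arm, with a missing indicator if preferred;
- include every mITT patient with a post-randomisation score;
- report the number without a usable Week 0 score by arm;
- keep the complete-baseline analysis as a sensitivity analysis.

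The cost is SAP wording and a few lines of code, with no new data. The small downside is a single-value fill for a covariate, which brings no gain if the baseline/Week 62 correlation exceeds about 0.7. With no missing baseline the treatment contrasts are identical to those now planned.

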The symptoms of UC must be recorded throughout the study, including the screening period. The e-diary entries will be reviewed by site personnel during screening (prior to dosing, if applicable) and during study visits, including the early withdrawal from treatment visit and any unscheduled visits due to disease exacerbation. Because the colonoscopy/flexible sigmoidoscopy and bowel cleansing preparations can interfere with the assessment of patient-reported symptoms, e-diary entries used to calculate the complete MCS should not correspond to days of bowel preparation or endoscopy or the day following the endoscopy. Further details and examples of stool frequency and rectal bleeding subscore derivation are provided in [Appendix 4](#).

Colonoscopy/Flexible Sigmoidoscopy with Colonic Biopsies

Patients are to prepare their bowel prior to the colonoscopy/flexible sigmoidoscopy procedures. Medications used for bowel preparation should be recorded on concomitant medications pages of eCRF.

Stool samples for analysis of fecal calprotectin and other exploratory biomarkers (such as analyses of the microbiota and bacterial cultures) are to be collected prior to bowel preparation (polyethylene glycol [PEG]–based preparation or enema).

Full colonoscopy within a year of screening is required to ensure against enrollment of patients with colonic carcinoma and dysplasia. If full colonoscopy has not been performed within the year before screening, it should be conducted in place of the flexible sigmoidoscopy at screening. For patients not requiring a colonoscopy, a flexible sigmoidoscopy will be performed on all patients for inclusion in the study. Endoscopy will be performed during screening 4–16 days prior to Day 1.

Endoscopy will be also performed at Weeks 10 and 62 and/or at withdrawal from study (early withdrawal from treatment visit, see [Appendix 1](#)).

Central reading of endoscopies will be performed throughout this study, and a detailed charter will address the standardization of endoscopic procedures, video recordings, and

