4.5.2.2 Assessments during Treatment

All assessments will be performed on the day of the specified visit, except where a time window is specified. Assessments scheduled on the day of study drug administration should be performed prior to dosing, unless otherwise noted. When study drug administration in the home is required on the same day as a clinic visit, drug is to be administered at home AFTER the clinic visit.

For induction (Week 10) and maintenance (Week 62) visits that are associated with an MCS requiring endoscopy, every effort should be made to schedule the endoscopy on the same day as the clinic visit. If this is not possible, endoscopy should be performed as close to the clinic visit as possible, with a maximal window of 3 days prior to and 5 days after the visit. The endoscopy score should be considered when determining the PGA (as applicable), a component of the MCS (see [Appendix 4](#)).

On a number of occasions during the Maintenance Phase (see [Appendix 1](#) and [Figure 3](#)), patients will be contacted by telephone for the purpose of study assessment, rather than making a clinic visit. During these telephone visits, data will be collected as for a clinic visit with the exception of blood sample and in clinic PRO assessments (see [Appendix 1](#), Schedule of Assessments). All adverse events and concomitant medications will be recorded and the patient questioned regarding a potential clinical relapse. An unscheduled visit is to be conducted as required (see Section [4.5.2.5](#)).

All patients will receive hands-on training in use of the e-diary and tablet. Patients will also be instructed to contact the site promptly if they have any questions about the use of the e-diary during screening or at any time during the study.

See [Appendix 1](#) for the schedule of assessments performed during the treatment period.

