Appendix 4 Mayo Clinic Score Measurement (cont.)

DATA COLLECTION REQUIREMENTS

Data will be collected on e-diary and other electronic media; during conversion to these media the format of the questions may change.

- A CRITICAL DATA POINT TAKEN AT BASELINE IS THE PATIENT'S NORMAL NUMBER OF STOOLS. This is defined as the number of stool passed when a patient is in remission/ not in flare. This is to be taken from the most recent available data in the patient's medical notes or taken during patient interview at screening. This value will remain stable throughout the study.
- Normal number of stools is to be rounded up (e.g., normal number of stools=1–2 would be rounded to 2)
- The NORMAL number of stools is to be recorded on the e-diary and made visible to the patient to assist with their scoring relative to this number

NOTE: Data recorded during bowel preparation procedures and day of endoscopy is to be ignored (bowel preparation and endoscopy procedure days are to be loaded onto the e-diary by the patient and excluded from the MCS calculation)

1. Stool frequency

- Stool frequency is to be recorded daily from start of screening to the end of the study in the e-diary
- The stool frequency is to be compared with the patient's normal stool frequency and entered as a score between 0 and 3 (see 1 above) (e.g., a patient normally has 1 stool per day and today has 4 stools. Therefore the patient has 3 stools more than "normal," which yields a value of 2 for that day.)
- The stool frequency will be defined as the passage of solid or liquid fecal material. Episodes of incontinence count. A non-productive trip to the bathroom or the simple passage of gas DOES NOT COUNT as stool.

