Appendix 4 Mayo Clinic Score Measurement (cont.)

- The post-baseline stool frequency value for endpoint assessment will be calculated as the average (rounded to the nearest integer) from the three most recent stool frequency scores that were entered in the e-diary within the 7 days prior to the clinic visit and prior to the days devoted to bowel preparation and endoscopy.

2. Rectal bleeding

- Rectal bleeding is to be recorded daily from screening to the end of the study in the e-diary
- The rectal bleeding score is to be categorized from 0–3 according to the definition given in 2 above
- Patients are to be instructed to ignore any blood which is caused by menstruation or hemorrhoids
- The baseline value for the rectal bleeding score will be taken from patient e-diary recordings that are entered between Day –22 (inclusive) and bowel preparation for the screening endoscopy and will be determined by the worst recording from the three most recent scores that were entered just prior to the day of bowel preparation. However, up to three post-endoscopy scores, starting with the score recorded 2 days after the endoscopy, may be used to calculate baseline rectal bleeding, but ONLY when fewer than three scores are available between Day –22 and bowel preparation (see [Figure 1](#) below). The days selected for this calculation are intended to prevent the use of rectal bleeding recordings during the screening period that are impacted by bowel preparation and endoscopy, including the day immediately following the endoscopy.
- The post-baseline rectal bleeding value for endpoint assessment will be determined by the worst of the three most recent rectal bleeding scores that were entered in the e-diary within the 7 days prior to the clinic visit and prior to the days devoted to bowel preparation and endoscopy.

3. Endoscopy Subscore

This score is provided by the endoscopy reading vendor as a subscore of 0 to 3.

- Findings on endoscopy will be documented by photographic evidence (central reading of endoscopy videos)
- The score will be based upon the worst affected segment (if mucosal appearance varies) *for study conduct, except at post-baseline time points, when the sigmoid colon MCS endoscopic subscore will be used if the baseline sigmoid colon MCS endoscopic subscore is 2–3.*

Note: The time window for performing endoscopy during the screening is 4–16 days prior to Day 1 (i.e., Day –16 to Day –4).

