##### **Rectal Bleeding Subscore 0–3**

- 0= No blood in stool
  - 1= Streaks of blood with stool less than half the time
  - 2= Obvious blood with stool most of the time
  - 3= Blood alone passed
- Stool Frequency (SF) subscore= Average of 3 days daily diary scores
- Rectal Bleeding (RB) subscore= Worst value of 3 days daily diary scores

[Table 2](#) summarizes the different scenarios for calculating SF/RB sub score in the analyses. The three days of daily diary data used to calculate the subscores described above are selected from the days most recent to, (but not including) a pre specified date, and this is called the 'anchor date'.

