**Table 2 Steps for Calculating SF/RB Subscore**

Timepoint	Scenarios to calculate SF/RB Subscore
Baseline	
Scenario 1 Bowel preparation date (prior to an endoscopy) is assigned as the ‘anchor’ date. Three days daily diary data collected from patient’s e-diary between Day -22 and the day prior to the anchor date will be selected to calculate SF/RB scores. Daily dairy days selected closest to the anchor date will be selected first

	
Scenario 2 Bowel preparation date (prior to an endoscopy) is assigned as the ‘anchor’ date. If fewer than three days of daily diary data are available between Day –22 through to the day prior to the anchor date, then additional daily diary data collected post endoscopy starting with the score recorded 2 days after the endoscopy but prior to the randomization/enrollment will be selected to calculate SF/RB scores. Examples of this scenario are illustrated (see Appendix 3).

	
Scenario 3 Randomization/Enrollment Date is assigned as the ‘anchor’ date, if endoscopy did not occur between Day -21 and day prior to randomization/enrollment date. Three days worth of diary data prior to the ‘anchor’ date will be selected to calculate SF/RB scores. Daily dairy days selected closest to the anchor date will be selected first

Post Baseline	
Scenario 1 Bowel preparation date (prior to an endoscopy) occurring within 7 days prior to the visit date is assigned as the ‘anchor’ date. Three daily diary days collected within the 7 days prior to post baseline visit date will be selected, to calculate SF/RB scores. Daily dairy days selected closest to the anchor date will be selected first. Visit date is the day the PGA assessment is collected.
 
Scenario 2 Bowel preparation date (prior to an endoscopy) is assigned as the ‘anchor’ date. Three daily diary days collected within the 7 days prior to post baseline visit date will be selected, to calculate SF/RB scores. Daily dairy days selected closest to the anchor date will be selected first.
 
If further days are required, data collected +2 days after endoscopy within the 7 days prior to visit date will be used. Visit date is the day the PGA assessment is collected.

	
Scenario 3 Visit date is assigned as the ‘anchor’ date. Three daily diary days collected within the 7 days prior to post baseline visit date will be selected, to calculate SF/RB scores. Daily dairy days selected closest to the anchor date will be selected first.

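### With the bowel-preparation date missing, project SAP 4.8 anchors the Mayo diary window on the endoscopy date, so a preparation-day entry can be scored and some Week 62 remitters counted as non-remitters

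*SAP*

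**What the plan says.** **Which days are scored.** Project SAP 4.4.2.1.1 takes three diary days, "selected from the days most recent to, (but not including) a pre specified date", the anchor. SF is their average and RB is the worst of the three. Protocol Appendix 4 adds that the SF average is rounded to the nearest integer.

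**The usual anchor.** In project SAP Table 2, post-baseline, "Bowel preparation date (prior to an endoscopy) occurring within 7 days prior to the visit date is assigned as the" anchor. The window is also fixed: "Three daily diary days collected within the 7 days prior to post baseline visit date will be selected". Because the anchor day is left out, the preparation day is not scored.

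**The fallback.** Project SAP 4.8, to avoid a missing score, says: "If bowel prep date is missing, then endoscopy date can be used". If the endoscopy date is missing too, the visit date may serve. Nothing there removes the day before endoscopy.

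**What the protocol requires.** Section 4.5.1.4 says "e-diary entries used to calculate the complete MCS should not correspond to days of bowel preparation or endoscopy", and it also bars the day after endoscopy. Appendix 4 limits post-baseline entries to those made "prior to the days devoted to bowel preparation and endoscopy".

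**Timing and source of the dates.** For Weeks 10 and 62, Protocol 4.5.2.2 says "every effort should be made to schedule the endoscopy on the same day as the clinic visit", with a limit of 3 days before to 5 days after. Under Appendix 4, "bowel preparation and endoscopy procedure days are to be loaded onto the e-diary by the patient".

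**The concern.** Anchoring on the preparation date is what keeps preparation out of the score. Moving the anchor to the endoscopy date makes the day before endoscopy the first day selected. Protocol Appendix 4 and project SAP Appendix 3 place preparation on exactly that day in their worked screening scenarios (endoscopy Day -16 with preparation Day -17; endoscopy Day -4 with preparation Day -5). The fallback can therefore bring in an entry that the protocol says must not be used.

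The primary endpoint is sensitive to this. Remission needs a Mayo Clinic Score (MCS) of 2 or less, every subscore at most 1, and RB 0, so one raised daily score can decide it. A score affected in this way looks like an observed failure. The tipping-point analysis keeps calculable non-remitters as non-remitters, and the partial and modified Mayo sensitivity analyses in study SAP 4.4.4 use the same SF and RB, so none of these planned checks would show it.

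**Working it through.** **1. The plan's own figure.** Protocol 6.1: 105 per arm, 25-point difference, placebo 30%–45%, two-sided 5%, power above 90%.

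Power = Φ[(d − 1.96·se0)/se1], where se0 = √(2·p̄(1−p̄)/n) and se1 = √((p1(1−p1)+p2(1−p2))/n).

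At 30% vs 55%: se0 = √(2×0.425×0.575/105) = 0.0682; se1 = √((0.2100+0.2475)/105) = 0.0660; (0.25 − 0.1337)/0.0660 = 1.76; power 96.1%. At 37.5% vs 62.5% it is 95.7%, and at 45% vs 70% it is 96.1%. The stated figure is confirmed.

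**2. Which days the fallback selects at Week 62.** Days are counted from the visit, with preparation on the day before endoscopy and the endoscopy date as anchor.

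| Endoscopy | Preparation | Days scored | Preparation scored? |
|---|---|---|---|
| 0 (default) | −1 | −1, −2, −3 | yes |
| −1 | −2 | −2, −3, −4 | yes |
| −2 | −3 | −3, −4, −5 | yes |
| −3 | −4 | −4, −5, −6 | yes |
| +1 to +5 | 0 to +4 | −1, −2, −3 | no |

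Under the second fallback (visit date, always days −1, −2, −3), the preparation day is scored when endoscopy was on day 0, −1 or −2. The endoscopy day is scored when it was on day −1, −2 or −3.

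**3. Effect on remission.** Seven patterns of SF, endoscopy (ES) and physician's global assessment (PGA) qualify with RB 0. Assume two ordinary days at the true SF plus one preparation day, with the protocol's rounding:
- True SF 0: preparation score 2 gives 2/3 = 0.67, rounded to 1; score 3 gives 3/3 = 1.
- True SF 1: preparation score 2 gives 4/3 = 1.33, rounded to 1; score 3 gives 5/3 = 1.67, rounded to 2.

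| SF/ES/PGA | True MCS | Preparation SF 2: SF, MCS | Preparation SF 3: SF, MCS |
|---|---|---|---|
| 0/0/0 | 0 | 1, 1 | 1, 1 |
| 0/0/1 | 1 | 1, 2 | 1, 2 |
| 0/1/0 | 1 | 1, 2 | 1, 2 |
| 0/1/1 | 2 | 1, 3 **lost** | 1, 3 **lost** |
| 1/0/0 | 1 | 1, 1 | 2, 2 **lost** |
| 1/0/1 | 2 | 1, 2 | 2, 3 **lost** |
| 1/1/0 | 2 | 1, 2 | 2, 3 **lost** |

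One of 7 is lost at a preparation score of 2, 4 of 7 at 3, and none at 0 or 1. Any preparation-day RB of 1 or more loses all seven, because RB is the worst of three days. The project SAP mentions only an average. Unrounded, a score of 2 would also lose 4 of 7 (SF 1.33 exceeds 1; 0.67+1+1 = 2.67 exceeds 2).

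**4. Error in the other direction.** With same-day endoscopy the window moves from −2, −3, −4 to −1, −2, −3, so day −4 is dropped. Suppose RB is 1 on day −4; SF and RB are 0 on days −2 and −3; and the preparation day has RB 0 and SF 2. The usual anchor gives RB 1, a non-remitter. The fallback gives RB 0 and SF 0.67, rounded to 1. With ES + PGA at most 1, the total is at most 2, a remitter.

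**5. How many patients.** Expected remitters at the planning rates: 105×(0.30+0.55) = 89 to 105×(0.45+0.70) = 121. The documents give no rate of missing preparation dates. Assuming 2–10%: 0.02×89 = 1.8 to 0.10×121 = 12.1, so about 2–12 exposed.

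**6. Power if a share of remitters is lost equally in both arms** (placebo 30% / 45%): 5% lost, 94.5% / 93.8%; 10% lost, 92.4% / 90.9%; 20% lost, 87.0% / 83.3%.

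**The case against.** **Recoverability.** Protocol 4.5.1.4 has preparation medication recorded on the concomitant-medication eCRF pages and site staff reviewing the diary at visits, so a missing date may be found. This stands, but project SAP 4.8 does not call for that search, and its permissive wording leaves the choice open.

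**Timing at Week 62.** Every scenario with preparation on the day before is a screening example, and Protocol 4.5.1.4 also mentions enema preparation. This stands as a limit: where preparation was on the endoscopy day, or endoscopy followed the visit, the preparation day is not scored.

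**What the fallback prevents.** Without it, a patient with no evaluable score would be a non-responder anyway (Protocol 6.4). That justifies having a fallback, but not one that admits an excluded day.

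**Stronger readings a reader might infer.**
- *That the fallback can only remove remitters.* Step 4 shows otherwise, since it also drops an earlier clean day.
- *That 2–10% of all 210 randomized patients (about 4–21) would be at risk of losing remission.* Only a patient otherwise in remission can lose it, so 89–121 is the base. The 4 of 7 is a count of patterns, not a proportion of patients.
- *That the treatment comparison is biased or underpowered.* The rule is blind to arm, and power exceeds 90% even if 10% of remitters are lost.
- *That an inflated screening score biases the comparison through Week 10 response.* Screening and Week 10 precede maintenance randomization, and both arms come from one open-label pool.

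**Conclusion.** The point holds as a contradiction between project SAP 4.8 and the protocol in deriving the primary endpoint. When the preparation date is missing, the day before endoscopy is scored, and where preparation was on that day an excluded entry enters the score. This covers the default same-day endoscopy and endoscopy up to 3 days before the visit. The main consequence is that some true remitters are counted as non-remitters, with occasional error the other way.

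The size is modest: about 2–12 patients exposed under an assumed 2–10% rate of missing dates, and fewer reclassified. The pattern counts assume a completed preparation-day entry, stable scores on the other days, a preparation-day SF of 2 or 3, and rounding as in the protocol. The documents do not support a claim that the trial's conclusion is threatened. The change is worth making because the rule conflicts with the protocol as written and is cheap to correct.

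**What to change.** Replace the fallback in project SAP 4.8 with a fixed rule:

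> If the bowel preparation date is missing, it is first sought from the bowel-preparation medication record on the concomitant medications eCRF. If still missing, the anchor date is the endoscopy date minus 1 day, and the endoscopy day and the day after are not used.

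With same-day endoscopy this scores days −2, −3 and −4, and all seven patterns in the working stay in remission. Where preparation was on the endoscopy day, one clean day is exchanged for the next earlier one.

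For an endoscopy score with no date, use the visit date minus 1 day and list these patients. This is only partial protection: if the undated endoscopy was 1–3 days before the visit, the preparation day would still be scored. The main rule also assumes a single preparation day, so a longer preparation would leave an earlier preparation day in the window.

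The cost is a short text change, a small change to the derivation, and a look-up in data already collected. A few patients may have one fewer usable diary day. The tightest case is endoscopy 3 days before the visit, where only days −5, −6 and −7 remain before the anchor.
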